7.3.13 Concomitant Medication

The use of any concomitant medication within the last 3 months prior to informed consent for participation in the trial (except medication used in previous infertility treatment cycles which will be recorded as part of the infertility history) and throughout the trial will be recorded. Recording of concomitant medication will be performed at all visits. Any changes in concomitant medications or treatments must be recorded at each visit.

7.3.14 Ultrasound for Image Acquisition of the Uterus

At a subset of trial sites, ultrasound for image acquisition of the uterus will be carried out at the transfer visit. Details on equipment and procedures related to this exploratory assessment will be provided in a trial-specific manual.

Resultant images may be analyzed to identify features that correlate with subject response to treatment and/or clinical outcomes, such as ongoing pregnancy. These data will be reported separately.

Supersedes: 5.0 Page 67 of 103

7.4 Assessments Related to Post-trial Information

7.4.1 Pregnancy Outcome and Neonatal Health Follow-up

All subjects with an ongoing pregnancy will be followed as part of the post-trial follow-up. Live birth rate and neonatal health data at birth covering gestational age, gender, birth weight and length, and Apgar scores after 1, 5 and 10 minutes will be collected. In addition, data on neonatal SAEs will be collected at 4 weeks and minimum 6 months after birth (see section 8.5.1). These data will be reported separately.

7.4.2 Late Pregnancy Loss

The occurrence of late pregnancy losses defined as an ongoing pregnancy (i.e. at least 1 intrauterine viable fetus at 8-9 weeks after blastocyst transfer), but no live birth will be evaluated as part of the post-trial follow-up. These data will be reported separately.

7.5 Handling of Biological Samples and Other Material

A trial-specific laboratory manual will be provided to the participating sites, describing in detail how to handle, store and transport the biological samples (blood) in this trial. All biological samples will be analyzed at central laboratories and will be maintained in storage after the end of the trial. Destruction will take place within 2 years after reporting of the trial or when methods / results have been adequately validated. An exception are the blood samples analyzed by a local laboratory at the trial clinic / hospital and subsequently destroyed. For all biological samples collected in the trial, it applies that analyses beyond those described in the protocol can only be performed after obtaining the required approvals. The processes related to handling of biological samples will be described in the informed consent documents, and biobank / data protection legislation including local legislation will be adhered to.

With respect to the image recordings of the uterus, a trial-specific manual will be provided to the subset of sites participating in this exploratory assessment, describing in detail the equipment and procedures. All recordings will be stored. Data protection legislation including local legislation will be adhered to.

Trial Code: 000303 E-Study Protocol-21539; Ver. 6.0

Supersedes: 5.0 Page 68 of 103

Date: 14 Oct 2019

8 **ADVERSE EVENTS**

8.1 **Adverse Event Definition**

An adverse event is any untoward medical occurrence in a subject participating in a clinical trial. It includes:

- Any unfavorable and unintended sign, symptom or disease temporally associated with the use of the IMP, whether or not considered to be caused by the IMP.
- Adverse events commonly observed and adverse events anticipated based on the pharmacological effect of the IMP.
- Any laboratory abnormality, vital sign or finding from physical or gynecological examination assessed as clinically significant by the investigator [note: pre-existing conditions diagnosed through assessments and examinations at the screening visit or during the screening period are not adverse events, but are recorded as medical history].
- Accidental injuries, reasons for any change in medication (drug and/or dose), reasons for any medical, nursing or pharmacy consultation, or reasons for admission to hospital or surgical procedures.

All adverse events will be coded by Ferring Global Pharmacovigilance using the Medical Dictionary for Regulatory Activities (MedDRA) (the version effective at trial start).

8.2 **Collection and Recording of Adverse Events**

8.2.1 **Collection of Adverse Events**

The investigator must monitor the condition of the subject throughout the trial from the time of obtaining informed consent until the end-of-trial visit.

The sources of adverse events cover:

- The subject's response to questions about her health (a standard non-leading question such as "How have you been feeling since your last visit?" is asked at each visit).
- Symptoms spontaneously reported by the subject.
- Investigations and examinations where the findings are assessed by the investigator to be clinically significant changes or abnormalities.
- Other information relating to the subject's health becoming known to the investigator (e.g. hospitalization).

8.2.2 **Recording of Adverse Events**

The investigator must record all adverse events in the Adverse Event Log provided in each subject's e-CRF with information about:

Trial Code: 000303 Date: 14 Oct 2019 E-Study Protocol-21539; Ver. 6.0 Supersedes: 5.0

Page 69 of 103

- Adverse event
- Date and time of onset
- Intensity
- Causal relationship to IMP
- Action taken to IMP
- Other action taken
- Date and time of outcome
- Outcome
- Seriousness.

Each of the items in the Adverse Event Log is described in detail in the following sections.

Adverse Event

Adverse events should be recorded as diagnoses, if available. If not, separate signs and symptoms should be recorded. One diagnosis/symptom should be entered per record.

If a subject suffers from the same adverse event more than once and the subject recovers in between the events, the adverse events should be recorded separately. If an adverse event changes in intensity, a worst-case approach should be used when recording the event, i.e. the highest intensity and the longest duration of the event.^b

Note: a procedure is not an adverse event; the reason for conducting the procedure is. Hospitalization is not an adverse event; the reason for hospitalization is. Death is not an adverse event, but the cause of death is (an exception is sudden death of unknown cause, which is an adverse event).

Date and Time of Onset

The date of onset is the date when the first sign(s) or symptom(s) were first noted. If the adverse event is an abnormal clinically significant laboratory test or outcome of an examination, the onset date is the date the sample was taken or the examination was performed.

Exception: if an adverse event with onset before the first IMP administration (i.e. a pre-treatment adverse event) worsens in intensity, this must be recorded as two separate events. The initial adverse event should be recorded with outcome "not recovered" and the date and time of outcome is when the intensity changed. The second adverse event should be recorded with date and time of onset when the intensity changed.

E-Study Protocol-21539; Ver. 6.0 Supersedes: 5.0 Page 70 of 103

Date: 14 Oct 2019

Intensity

The intensity of an adverse event must be classified using the following 3-point scale:

Mild: Awareness of signs or symptoms, but no disruption of usual activity.

Moderate: Event sufficient to affect usual activity (disturbing).

Severe: Inability to work or perform usual activities (unacceptable).

Causal Relationship to IMP

The possibility of whether the IMP caused the adverse event must be classified as one of the following:

Reasonable possibility:

There is evidence or argument to suggest a causal relationship between the IMP and the adverse event. The adverse event may occur as part of the pharmacological action of the IMP or may be unpredictable in its occurrence.

Examples:

- Adverse events that are uncommon but are known to be strongly associated with IMP exposure.
- Adverse events that are not commonly associated with IMP exposure, but the event occurs in association with other factors strongly suggesting causation, such as a strong temporal association or the event recurs on rechallenge with the IMP.

No reasonable possibility:

There is no reasonable evidence or argument to suggest a causal relationship between the IMP and the adverse event.

Examples:

- Known consequences of the underlying disease or condition under investigation.
- Adverse events common in the trial population, which are also anticipated to occur with some frequency during the course of the trial, regardless of IMP exposure.

Date: 14 Oct 2019 E-Study Protocol-21539; Ver. 6.0 Supersedes: 5.0 Page 71 of 103

Action Taken to IMP

The action taken to the IMP in response to an adverse event must be classified as one of the following:

- No change (medication schedule maintained or no action taken)
- Discontinued
- Interrupted
- Dose reduced
- Dose increased.

Other Action Taken

Adverse events requiring therapy must be treated with recognized standards of medical care to protect the health and well-being of the subject. Appropriate resuscitation equipment and medicines must be available to ensure the best possible treatment of an emergency situation.

If medication is administered to treat the adverse event, this medication should be entered in the Concomitant Medication Log.

Date and Time of Outcome

The date and time the subject recovered or died.

Outcome

The outcome of an adverse event must be classified as one of the following:

- Recovered (fully recovered or the condition has returned to the level observed at initiation of trial treatment)
- Recovered with sequelae (resulted in persistent or significant disability/incapacity)
- Recovering (the event is improving)
- Not recovered
- Fatal.

Trial Code: 000303

E-Study Protocol-21539; Ver. 6.0 Supersedes: 5.0 Page 72 of 103

Date: 14 Oct 2019

8.3 Adverse Events of Special Interest

8.3.1 Ovarian Hyperstimulation Syndrome

Symptoms and Classification

Mild OHSS

OHSS is an adverse event of special interest during controlled ovarian stimulation. Investigators will record OHSS symptoms using a classification system based on Golan's classification system¹³ as shown in Table 8-1 to grade (1, 2, 3, 4 or 5) each OHSS case.

Table 8-1 Classification of Mild, Moderate and Severe OHSS (Golan's Classification System)

Grade 1	Abdominal distension and discomfort							
Grade 2	Features of grade 1 plus nausea/vomiting and/or diarrhea. Ovaries enlarged to 5-12 cm. ^{a)}							
Moderate OHSS								
Grade 3	Features of mild OHSS plus ultrasonic evidence of ascites. ^{b)}							
Severe OHSS								
Grade 4	Features of moderate OHSS plus clinical evidence of ascites and/or hydrothorax (or breathing difficulties). Paracentesis due to OHSS symptoms. c)							
Grade 5	All of the above plus change in blood volume, increased blood viscosity due to hemoconcentration, coagulation abnormalities, and diminished renal perfusion and function. d) Hospitalization due to OHSS symptoms. e)							

- ^{a)} For each ovary, the size will be the average of the greatest diameter and its greatest perpendicular diameter. Ovarian enlargement will be based on the average size of the right and left ovaries. The sizes of both ovaries should be recorded.
- b) For subjects with transvaginal evidence of ascitis, the size of the fluid pockets in the pelvis (Douglas pouch, vesicouterine pouch, etc.) should be estimated by measuring the greatest diameter and its greatest perpendicular diameter, and multiplying these two numbers (the unit will be cm²). Peritoneal fluid is the total size of all fluid pockets in the pelvis.
- c) In case of paracentesis, the volume of fluid drained should be measured.
- d) Hemoconcentration is defined as hematocrit >45 %. Electrolyte disturbances is defined as hyponatremia (sodium <135 mEq/L) and/or hyperkalemia (potassium >5.0 mEq/L). Coagulation abnormalities are defined as presence of thromboembolic events, abnormal prothrombin time or abnormal activated partial thrombin time. Diminished renal perfusion is defined as creatinine >1.2 mg/dl. Oliguria is defined as urine output less than 500 mL / 24 hours. Anuria is defined as failure to produce urine. If applicable, actual volume of urine output will be recorded.
- e) Hospitalization is defined as admission exceeding 24 hours.

All cases of OHSS must be reported as adverse events and followed until the adverse event has an outcome of recovered. Any case of OHSS that requires hospitalization or surgical/medical intervention should be considered severe. All cases of severe OHSS should be reported as a SAE.

Supersedes: 5.0 Page 73 of 103

Please note, that the classification of 'mild OHSS', 'moderate OHSS' and 'severe OHSS' does not refer to the classification of an adverse event's intensity (also rated mild, moderate, or severe), but to the grades in Golan's Classification System described above.

Subject narratives will be prepared for all OHSS cases.

Concerning timing, early OHSS will be defined as OHSS with onset ≤ 9 days after triggering of final follicular maturation and late OHSS will be defined as OHSS with onset ≥ 9 days after triggering of final follicular maturation.

Preventive Interventions of Early OHSS

Preventive interventions of early OHSS include the following:

- Cycle cancellation due to excessive ovarian response
- Administration of dopamine agonist (only in subjects with ≥ 20 follicles of ≥ 12 mm)
- Investigator requested reduction in gonadotropin dose to prevent OHSS

Investigations in case of OHSS

The investigator should report signs, symptoms and laboratory assessments used to diagnose and classify all cases of OHSS in the e-CRF. The following investigations must be conducted when OHSS symptoms are first observed and repeated when there are clinically relevant changes in the OHSS presentation:

- Body weight and maximum abdominal circumference
- Ultrasound of ovarian size and if applicable, measurement of pelvic/abdominal/thoracic fluid
- Vital signs
- Blood sample for central lab analysis of the following:
 - Progesterone and estradiol
 - Red blood cell count, white blood cell count, hemoglobin, hematocrit, platelet count and differential count
 - Alanine aminotransferase, aspartate aminotransferase, blood urea nitrogen, calcium, chloride, creatinine, gamma-glutamyl transferase, non-fasting glucose, potassium and sodium
 - Coagulation parameters (prothrombin time, activated partial thrombin time)

> Supersedes: 5.0 Page 74 of 103

Any treatments of OHSS, e.g. intravenous administration of volume expanders, paracentesis, use of low-molecular-weight heparin and intravenous administration of albumin, must be recorded as concomitant medication.

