10.2.2 OHSS

OHSS for each treatment group will be tabulated by classification (mild, moderate, severe) and grade (1, 2, 3, 4, 5). These tabulations will be made for OHSS overall as well as separately for early OHSS and late OHSS.

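### Protocol 8.3.1 gives two rules for severe OHSS that disagree for some grade 1–3 cases requiring intervention, and neither document says which one sets the tabulated class

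*Protocol*

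**What the plan says.** Protocol 8.3.1 tells the investigator to use a system based on Golan's classification, "as shown in Table 8-1 to grade (1, 2, 3, 4 or 5) each OHSS case". In Table 8-1, grades 1 and 2 are mild, grade 3 is moderate, and grades 4 and 5 are severe. Grade 3 is defined by features alone: "Features of mild OHSS plus ultrasonic evidence of ascites". Grade 4 combines "Features of moderate OHSS plus clinical evidence of ascites and/or hydrothorax (or breathing difficulties") with "Paracentesis due to OHSS symptoms". Grade 5 includes "Hospitalization due to OHSS symptoms", and footnote e limits hospitalization to admissions longer than 24 hours.

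The text after the table adds a second rule: "Any case of OHSS that requires hospitalization or surgical/medical intervention should be considered severe". It sets no condition on grade and does not define medical intervention. It is followed by an instruction that every severe case be reported as an SAE. The next paragraph says that mild, moderate and severe OHSS are not adverse event intensity but refer to the "grades in Golan's Classification System described above".

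SAP 10.2.2 states: "OHSS for each treatment group will be tabulated by classification (mild, moderate, severe) and grade (1, 2, 3, 4, 5"). Protocol 9.8.3 plans the same tabulation. Both repeat it for early and late OHSS, and neither gives a derivation or precedence rule. Protocol 7.2.12 only refers back to section 8.3.

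**The concern.** Both rules apply to every OHSS case, and for some cases they give different answers. A site following the table would call a grade 2 or grade 3 case mild or moderate. A site following the sentence would call the same case severe if it required medical intervention. With up to 25 centers and no definition of medical intervention, sites may not draw the line in the same place.

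Two outputs depend on the answer. The first is the split of OHSS by class, where OHSS frequency is a secondary endpoint and OHSS is the adverse event of special interest. The second is the SAE count, because the severe label alone triggers SAE reporting. The tabulation could also contradict itself, with the severe count in the classification rows differing from the total of grades 4 and 5 in the grade rows.

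**Working it through.** The plan states no OHSS rate, so there is no figure to reproduce. The check sets the two rules side by side.

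| Case | Table 8-1 | Intervention sentence | Agree? |
|---|---|---|---|
| Paracentesis for OHSS symptoms | Grade 4, severe | Severe | Yes |
| Hospitalization over 24 hours for OHSS symptoms | Grade 5, severe | Severe | Yes |
| Grade 1–2 features, requires non-surgical treatment | Mild | Severe | No |
| Grade 3 features, requires non-surgical treatment | Moderate | Severe | No |
| Grade 1–3 features, requires surgery other than paracentesis | Mild or moderate | Severe | No |
| Grade 1–3 features, admitted for 24 hours or less | Mild or moderate | Severe, unless footnote e is carried over to the sentence | Depends |

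The disagreement on non-surgical treatment is one the protocol itself foresees. Section 8.3.1 names intravenous volume expanders, low-molecular-weight heparin and intravenous albumin as OHSS treatments to be recorded. None of them is a grading criterion in Table 8-1.

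The paragraph tying the labels to the Golan grades does not settle the matter. If severe means grade 4 or 5, the sentence must either raise the recorded grade or contradict the table. The protocol does not say that the grade is raised, or to which level.

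Scale of one changed case, with arm sizes from Protocol 3.2 and 9.1 and all randomized subjects assumed treated:

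- Change in an arm's severe rate = 1 / subjects in the arm.
- Planned size: 1/200 = 0.5 percentage points.
- Maximum size after sample size reassessment: 1/250 = 0.4 percentage points.

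The number of such cases cannot be found in the documents. For an assumed range of 1 to 5 per arm, the shift is 0.5 to 2.5 points at 200 per arm (5/200 = 2.5%) and 0.4 to 2.0 points at 250 (5/250 = 2.0%). The total number of OHSS cases is the same under either rule.

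**The case against.** The best case for the plan is that the sentence is a deliberate escalation added to the table, or an SAE trigger. It stands between two reporting instructions, and Protocol 8.5.1 already treats some events needing intervention as serious. On that view both rules apply and sites need not choose. The rules also largely overlap, because the table itself places paracentesis and longer hospitalization at severe grades.

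The overlap stands and limits the point. The coherent reading is possible but is not written down. Nothing labels the sentence as a reporting trigger only. If it is an escalation, the recorded grade is left open, and the following paragraph ties the class to that grade.

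It is also fair that the planned summaries are descriptive, that grade is shown next to class so a grade-based severe count can be read off, and that every OHSS case gets a narrative.

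Three stronger inferences are tempting and unsupported. A reader might take any treated case to be severe. The sentence says requires, and the treatments that 8.3.1 names are substantial ones. A reader might infer that the severe rate could multiply. That needs an OHSS rate, a grade distribution and a share requiring treatment, and the documents give none of these. A reader might infer bias between arms. Treatment is double-blind and randomization is stratified by site, so differences in how readily sites treat should not systematically favor one arm.

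**Conclusion.** The point holds as an internal contradiction with limited reach. For grade 1–3 cases that require non-surgical treatment, surgery other than paracentesis, or (if footnote e does not govern the sentence) a short admission, Protocol 8.3.1 supports two different classes. The planned tabulation can show the same subject as severe and as grade 1, 2 or 3.

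Each such case moves an arm's severe rate by 0.5 percentage points at 200 per arm, or 0.4 at 250, and can add one SAE unless the case is serious on other grounds. How many cases would be affected is unknown. Total OHSS frequency, which is the secondary endpoint as worded, and the primary analysis do not change. What suffers is the consistency of a descriptive safety table and of the SAE count. The conclusion rests on the protocol and SAP alone; an e-CRF completion guideline might settle the question, but none is among the documents.

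**What to change.** Reconcile Table 8-1 with the intervention sentence in Protocol 8.3.1. State whether the sentence sets the OHSS classification, and if so which grade is then recorded, or whether it serves only as a trigger for SAE reporting. Say what counts as medical intervention and whether footnote e applies to the sentence. Which rule is right is for the sponsor to decide.

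In SAP 10.2.2, state before unblinding the single derivation of classification that follows from that decision, so that class and grade agree for every subject. Add a separate row by arm for OHSS with hospitalization or surgical/medical intervention, which keeps that information visible whichever rule is chosen.

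The cost is about one sentence in each document and one table row. No new collection should be needed: diagnostic findings go into the e-CRF, OHSS treatments are recorded as concomitant medication and are listed source data (Protocol 10.1), and all OHSS cases have narratives.

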8.4 Other Events of Special Interest

8.4.1 Injection Site Reactions

Injection site reactions after administration of IMP (MENOPUR liquid including Placebo to MENOPUR powder and MENOPUR powder including Placebo to MENOPUR liquid) are only to be reported as adverse events if they require active management, i.e. discontinuation of IMP, additional investigations or treatment of the injection site reaction. Local tolerability of IMP constitutes a secondary endpoint and will be evaluated in detail based on the subjects' recordings in the diary.

Local tolerability reactions after administration of NIMP are to be reported as adverse events if they fulfil the definition of an adverse event.

8.4.2 Treatment-induced Anti-MENOPUR Antibodies

Presence of treatment-induced anti-MENOPUR antibodies is not to be reported as an adverse event. These data will be described as part of the secondary endpoints.

8.4.3 Menstrual Bleeding

Menstrual bleeding is only to be reported as an adverse event in case it is excessive, painful, delayed or in any other way deviating from the subject's normal menstruation. Menstrual bleeding associated with lack of pregnancy will be reported as part of the efficacy evaluation.

